11.8.3 Statistical Power for Comparing Two Regimens within one Indication

If more than one regimen is evaluated for the same indication in two different cohorts in the expansion part, the response rates in the two cohorts will be compared as described in Section 11.5.1.2). The power (probability of being able to detect a statistically significant difference between two regimens A and B with underlying true response rates θ_A , and θ_B , respectively) for different stages of sample sizes, is presented in Table 11-9. It is noted that the sample sizes at the final analysis may not be equal.

For each scenario, 50,000 trials were simulated, and the logistic regression model (see Section 11.5.1.2) was estimated using SAS PROC GENMOD to test the significance (at the one-sided Type I error rate of 5%) of Regimen *B* being better than Regimen *A*. The power is the percentage of trials were the p-value of the regimen effect was <5% (one-sided). The simulations are constrained on having at least two responders in each cohort at N=20, and at least four responders in each cohort at N=40 and N=60. This reflects the expansion strategy within each cohort and implies that there is some similarity imposed on the realized trials that impacts the following power assessment.

θ_A	$ heta_B$	Power	Power	Power	
		$@N_A = N_B = 20$	$@N_A = N_B = 40$	$@N_A = N_B = 60$	
10%	15%	0%	0%	6%	
10%	20%	2%	5%	24%	
10%	25%	6%	18%	52%	
15%	20%	1%	3%	9%	
15%	25%	4%	11%	26%	
15%	30%	10%	27%	49%	
20%	25%	2%	5%	9%	
20%	30%	6%	15%	23%	
20%	35%	13%	30%	45%	
25%	30%	4%	7%	8%	
25%	35%	8%	15%	22%	

Table 11-9: Power	(Probability to	Detect a S	Significant	Difference	Between tw	wo Regimens)
	· ·		8			

Due to foreseen scenarios and the constraint imposed on the simulations, the probability to conclude that there is a significant improvement with Regimen B over Regimen A is low to moderate. The power ranges from 0% up to 52%, depending on the underlying assumed response rates and the sample sizes. This can also be expressed as that the probability of not being able to detect a difference based on the statistical model lies between 48 and 100%.

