11.8.2 Expansion Cohorts

The maximum sample size for each expansion cohort is 60 patients, divided over up to 4 stages as described in Section 11.7. The historical (p_0) and target (p_1) response rates being used to evaluate the operating characteristics are presented in Table 11-6.

	Colorectal Cancer (CRC)	Triple Negative Breast Cancer (TNBC)	Other indications*	
Historical response rate (p ₀)	2%	7.5%	10%	
Target response rate that warrants further evaluation of the drug (p ₁)	15%	20%	25%	
the drug (pl)				

Table 11-6: Response Rate Characteristics by Indication

*NSCLC, RCC, gastric, pancreas or urothelial cancer

Given p_0 and p_1 it is possible to prospectively calculate the required number of responders to further explore each stage as presented in Table 11-7. A priori it is assumed that the response rate is distributed as Beta(0.2, 0.8).

Table 11-7: Cont	tinuation Criteri	a in Terms of	Number of 1	Responders
------------------	-------------------	---------------	-------------	------------

Indication	Stage 2 (n=10; N=20)	Stage 3 (n=20; N=40)	Stage 4 (n=40; N=60)
CRC	≥1/10	≥2/20	≥4/40
TNBC	≥1/10	≥2/20	≥6/40
Other	≥1/10	≥3/20	≥7/40

Numbers of responses serve as a guideline; however, the totality of efficacy data will be considered when making decisions to terminate or continue an arm.

The operating characteristics in terms of the probability for not exploring a stage, and the probability that the estimated response rate is greater than p_1 (if the stage is completed) are presented in Table 11-8. The operating characteristics are based on 50,000 simulations of each assumption of true response rate. For the colorectal cohort there is a high probability to stop under p_0 early on, which partly is due to the requirement to beat p_1 (15%) with some confidence as well. This requirement has less impact on the TNBC cohort and the other indications (NSCLC, RCC, gastric, pancreatic and urothelial cancer) for which the stopping rate is lower.

Table	11-8	: Opera	ting C	Charac	teristics	in	Terms	of a)	Prob	ability	for 1	not E	Explor	ing	each
Stage;	and	b) the	Proba	bility 1	that the	Est	imated	Resp	onse	Rate is	Gre	ater	than	p1 (i	f the
Stage	is Co	mpleted	l)												

Indication	True ORR	Stage 2		Stage 3		Stage 4	
		(n=10; N=20)		(n=20; N=40)		(n=40; N=60)	
		a)	b)	a)	b)	a)	b)
CRC	2%	81%	1%	94%	0%	99%	0%
(p ₀ =2%; p ₁ =15%)	15%	20%	56%	18%	54%	13%	55%
TNBC	7.5%	46%	6%	55%	1%	92%	0%
$(p_0=7.5\%; p_1=20\%)$	20%	11%	58%	7%	56%	16%	54%

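### Table 11-9 applies the CRC responder minima to every indication, so its power figures are too high for TNBC and the other indications where the weaker regimen has a low response rate, and its stated alpha does not match its numbers

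*Protocol*

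**What the plan says.** Protocol Section 11.8.3 simulates the comparison of regimens A and B at 20, 40 and 60 patients per cohort. Only trials with "at least two responders in each cohort at N=20, and at least four responders in each cohort at N=40 and N=60" are kept, and the reason given is "This reflects the expansion strategy within each cohort". Significance is judged "at the one-sided Type I error rate of 5" per cent. Table 11-9 is not split by indication. From it the section concludes that power runs from 0% to 52%, so that a true difference is missed with probability 48% to 100%.

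The expansion rule itself is in Section 11.8.2, which sets out "the required number of responders to further explore each stage as presented in Table 11-7":

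- "CRC ≥1/10 ≥2/20 ≥4/40"
- "TNBC ≥1/10 ≥2/20 ≥6/40"
- "Other ≥1/10 ≥3/20 ≥7/40"

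The section adds that "Numbers of responses serve as a guideline". Section 11.5.1.2 plans the regimen comparison as a logistic regression adjusted for ECOG score, tested at a two-sided 5% level.

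**The concern.** The pair of minima used in the simulation (2 at 20, 4 at 40) is the CRC row of Table 11-7 and no other row. Yet the response rates in Table 11-9 start at 10%, so CRC's historical rate of 2% never appears. The 52% row (10% vs 25%) is exactly the historical and target pair that Table 11-6 gives for the other indications.

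A higher minimum removes the trials in which regimen A does worst, and those are the trials in which a difference is easiest to detect. Conditioning on too low a minimum therefore makes conditional power look better than the design's own rule implies. The comparison is meant to help choose a regimen for further development, so its power should be right for the indication in question.

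**Working it through.** **Inputs.** Response rates, cohort sizes and printed power are from Table 11-9; minima are from Section 11.8.3 and Table 11-7; the two-sided 5% level is from Section 11.5.1.2. Table 11-7 has no criterion at 60, so the 40-patient minimum is carried to 60, as the protocol does with 4.

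**Formula.** With x_A and x_B independent binomials of size n, the Wald statistic for the log odds ratio is

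z = ln[x_B(n − x_A) / (x_A(n − x_B))] / √[1/x_A + 1/(n − x_A) + 1/x_B + 1/(n − x_B)].

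Conditional power = P(z > c, x_A ≥ m, x_B ≥ m) / P(x_A ≥ m, x_B ≥ m). Here c = 1.96 for two-sided 5% (B better) and 1.645 for one-sided 5%. The sums are exact. ECOG is left out.

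**Step 1: reproduce the table.** With m = 2, 4, 4 and c = 1.96, all 33 cells agree to within 0.7 point; the 52% cell gives 51.8%. With c = 1.645, as Section 11.8.3 states, that cell would be 66.8%. So the table was computed at two-sided 5%. An ECOG-adjusted simulation (assuming half the patients are ECOG 1 and ECOG has no effect, 6,000 runs) gave 49.8% and 64.6%, which leads to the same conclusion.

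**Step 2: change only the minima.** For 10% vs 25%, two-sided 5%:

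| n per cohort | Printed | CRC minima | TNBC minima | Other minima |
|---|---|---|---|---|
| 20 | 6% | 6.3% | 6.3% | 2.8% |
| 40 | 18% | 17.9% | 7.4% | 3.9% |
| 60 | 52% | 51.8% | 36.5% | 28.5% |

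The denominator at n = 60, P(both cohorts reach the minimum), falls from 0.863 (4 responders) to 0.562 (6) and 0.392 (7). The largest power in the table becomes 44.8% for TNBC (15% vs 30%) and 43.3% for the other indications (20% vs 35%). The probability of missing a difference then starts at 100 − 44.8 = 55.2% and 100 − 43.3 = 56.7%, not 48%.

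The effect depends on regimen A's rate. At n = 60 with 20% or more it is about 2 points at most: under the other indications' minima, 20% vs 35% moves from 45% to 43% and 20% vs 30% from 23% to 22%. At n = 40 it remains larger: under the same minima, 20% vs 35% falls from 30% to 17.5%.

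**Step 3: apply the rules in sequence (a separate matter).** The table conditions on the final count only. Applying each Table 11-7 row at 10, 20 and 40 patients, for 10% vs 25%, two-sided 5%:

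| Rule | P(A reaches 60) × P(B reaches 60) | Power if both reach 60 | Overall power, unequal sizes allowed |
|---|---|---|---|
| CRC | 0.410 × 0.931 = 38.2% | 41% | 26% |
| Other | 0.080 × 0.833 = 6.6% | 18% | 11% |

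Overall power counts a cohort with no responders as no detection. Table 11-8 points the same way: at a true 10%, it shows a 90% chance that an other-indication cohort fails the Stage 4 criterion.

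**The case against.** A reader might take 18% or 11% against the printed 52% as the cost of using CRC minima. The documents do not support that. The like-for-like figure is 28.5%; the rest comes from sequential stopping and from dropping the condition that both cohorts finish. CRC under its own rule falls too, to 41% and 26%.

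A reader might also infer that power is overstated throughout for six of the seven indications because the weaker regimen usually stops early. That is too broad. TNBC shares the CRC minimum at 20. Under the other indications' rule, the chance of stopping before 60 is 92% at a true 10% and 67% at 15%, but 37% at 20% and 17% at 25%. Under the TNBC rule it is 50% at 15% and 23% at 20%. For 25% vs 30%, overall power is 8.3% for both groups against 8% printed.

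The alpha conflict works in the opposite direction. At the one-sided 5% the section states, overall power under the other indications' rule would be 51% for 20% vs 35%, above the printed 45%.

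In the plan's favour, Section 11.8.3 discloses the constraint, warns that it affects the power and that final sizes may differ, and calls the power low to moderate. The responder numbers are guidance, cohort size is set by the predictive-probability rule rather than this table, and SAP Section 3 records that the expansion part was not initiated. All of this lowers the consequence. None of it makes the CRC minima the expansion rule for the other six indications.

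**Conclusion.** The point stands as a correction to a stated power. The minima match CRC only, and replacing them with the right row takes the 52% cell to 36.5% (TNBC) or 28.5% (other indications), a drop of about 15 or 23 points. The change is large where regimen A responds at 10% to 15%, and small at 60 per cohort where it responds at 20% or more. Separately, the table leaves out sequential stopping and unequal final sizes, and its stated one-sided test is not the one used. At one-sided 5% the gap between indications remains: 66.8%, 54.6% and 45.1% for CRC, TNBC and other.

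These figures assume that the guideline criteria are followed, that ECOG has no effect on response, and that the 40-patient minimum carries to 60. No sample size or decision rule depends on the table.

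**What to change.** State one alpha in Section 11.8.3. The two-sided 5% of Section 11.5.1.2 is the natural choice, since the table already uses it. Re-run Table 11-9 separately for CRC, TNBC and the other indications, with each Table 11-7 row applied in sequence at 10, 20 and 40 patients. Report overall power, with unequal final sizes allowed, beside the power conditional on both cohorts completing. Then restate the sentences giving the maximum power of 52% and the 48% to 100% chance of missing a difference.

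The cost is a short simulation and a less favourable table, with no extra patients. Because the expansion part was not opened, the correction matters for the protocol record and for any reuse of the design.

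### Table 11-9 sets the responder minimum at the end of each stage instead of at the look that opens it; at two-sided 5% the highest power is about 42%, not 52%

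*Protocol*

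**What the plan says.** Protocol Section 11.8.2 states that, given the historical and target rates, "it is possible to prospectively calculate the required number of responders to further explore each stage as presented in Table 11-7". The column headings of that table give n, the sample size at the interim look, and N, the sample size at the end of the stage; Table 11-3 defines both. The rows are:

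- "CRC ≥1/10 ≥2/20 ≥4/40"
- "TNBC ≥1/10 ≥2/20 ≥6/40"
- "Other ≥1/10 ≥3/20 ≥7/40"

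A CRC cohort therefore goes on to N=20 with at least 1 response in 10, to N=40 with at least 2 in 20, and to N=60 with at least 4 in 40.

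Section 11.8.3 keeps a simulated trial if there are "at least two responders in each cohort at N=20, and at least four responders in each cohort at N=40 and N=60". It justifies this with "This reflects the expansion strategy within each cohort". It describes the test as run "at the one-sided Type I error rate of 5" per cent, whereas Section 11.5.1.2 plans a two-sided 5% test of the odds ratio. It summarises Table 11-9 as "The power ranges from 0% up to 52%, depending on the underlying assumed response rates and the sample sizes", and puts the chance of missing a difference at 48% to 100%.

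**The concern.** At N=20 and N=40 the simulated condition is the CRC rule for leaving the stage, not for entering it. At N=60 the condition, at least 4 in 60, appears nowhere in Table 11-7. The actual gate is at least 4 in the first 40, followed by 20 more patients.

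The difference matters most for a weak regimen. A cohort with a true rate of 10% meets 4 in 60 about 86% of the time, but meets 4 in 40 only about 58% of the time. A weak cohort that does reach N=60 has usually been lucky in its first 40 patients, so its observed rate is raised and the contrast with the better regimen shrinks. A condition on the final 60 misses most of this selection.

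The planned comparison is one of the inputs to choosing a regimen for further development (Section 11.5.1.2). At stake is whether the quoted power describes the design in Tables 11-3 and 11-7.

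**Working it through.** **Inputs.** Response rates and printed power come from Table 11-9, stage minima from Table 11-7, and the final-count minima (2, 4, 4) and stated test level from Section 11.8.3. The planned test level is in Section 11.5.1.2, and allocation is 1:1 (Section 6.1.2).

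**Method.** Enumerate two independent binomial cohorts exactly. With a and b responders out of N per cohort, the logistic-regression Wald statistic without covariates is

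z = ln[b(N−a) / (a(N−b))] / √(1/a + 1/(N−a) + 1/b + 1/(N−b)).

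Power = P(z > critical value and both cohorts meet the condition) / P(both cohorts meet the condition). The critical value is 1.96 for two-sided 5% in favour of B, and 1.645 for one-sided 5%.

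**Step 1: reproduce the plan.** With the minimum on the final count only and 1.96, all 33 cells reproduce, with a largest difference of 0.7 points. The 10% v 25% row gives 6.3/17.9/51.8 against the printed 6/18/52. With the same condition at 1.645, that row gives 66.8% at N=60, and only 1 of the 33 cells matches. Likelihood-ratio and score tests, joint instead of conditional power, and other placements of the minimum were also tried; none reproduces the whole table. The table was therefore evidently run at two-sided 5%, not at the level stated.

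**Step 2: check the looks.** The probability of falling short of each Table 11-7 minimum at n=10, 20 and 40 reproduces column a) of Table 11-8 to within 1 point. For CRC at a true rate of 15% it is 19.7/17.6/13.0% against the printed 20/18/13%. Section 11.8.2 thus does use the minima at the looks.

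**Step 3: move the minima to the looks.** CRC rule (≥1/10, ≥2/20, ≥4/40), two-sided 5%, power in % at N=20/40/60:

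| A v B | Printed | CRC looks |
|---|---|---|
| 10 v 15 | 0/0/6 | 0.9/2.8/3.8 |
| 10 v 20 | 2/5/24 | 3.5/10.9/16.9 |
| 10 v 25 | 6/18/52 | 9.5/26.5/41.2 |
| 15 v 20 | 1/3/9 | 1.9/4.2/6.0 |
| 15 v 25 | 4/11/26 | 5.6/12.9/19.8 |
| 15 v 30 | 10/27/49 | 12.2/28.1/42.2 |
| 20 v 25 | 2/5/9 | 3.0/5.4/7.3 |
| 20 v 30 | 6/15/23 | 7.0/14.1/20.7 |
| 20 v 35 | 13/30/45 | 13.3/28.1/41.6 |
| 25 v 30 | 4/7/8 | 3.7/6.0/7.8 |
| 25 v 35 | 8/15/22 | 7.5/14.2/20.3 |

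The maximum is 42.2%, so the chance of missing a difference starts at 100 − 42.2 = 57.8%, not 48%.

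**Step 4: other rules.** For 10% v 25% at N=60, the TNBC looks give 25.3% and the looks for other indications give 18.1%.

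**Step 5: how often the comparison arises.** For 10% v 25% under the CRC looks, both cohorts reach N=60 in 38.2% of trials. The probability of both reaching N=60 and the test being significant is 0.382 × 0.412 = 15.7%.

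**Step 6: ECOG adjustment.** Monte Carlo with an ECOG term (3,000 trials each; ECOG assumed 50/50 with no effect) gives 51% with the final-count condition and 40% with the CRC looks. The covariate does not explain the gap.

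**The case against.** **The sentence could be read cumulatively**: at least 2 at 20, at least 4 at 40 and at least 4 at 60. For N=60 that is close to the real CRC gate, so the fault could lie in the program and not in the description. But this reading gives 41.0% for 10% v 25% at N=60, so it does not rescue the printed 52%. At N=20 and N=40 the condition remains an exit rule.

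**The result depends on the test level.** This stands. At the one-sided 5% that Section 11.8.3 states, the CRC looks give 57.3% for the same cell, above the printed 52%. The like-for-like fall at that level is from 66.8% to 57.3%. A reader might infer that 52% is too high whatever the level; it is too high only at two-sided 5%, the level planned in Section 11.5.1.2 and the one at which the table reproduces.

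**The 52% might be taken as the CRC figure.** The Protocol does not label it so. Table 11-9 is not split by indication, 10%/25% is the historical/target pair for the other indications in Table 11-6, and CRC's own pair (2%/15%) is in no row. Only the minima 2 and 4 match CRC's thresholds, and CRC's rule is the most lenient of the three.

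**The practical consequence is small.** This also stands. Section 11.8.2 calls the thresholds a guideline, Section 11.8.3 already describes power as low to moderate, and neither 52% nor 41% is adequate power. Cohort sizes come from the stage rules, not from Table 11-9, and SAP Section 3 says the expansion part was not initiated. None of this makes the printed figures right for the design they claim to describe.

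**Conclusion.** The point holds. Table 11-9 conditions on the wrong sample sizes, and the statement that the constraint reflects the expansion strategy is incorrect. Against the printed cells, at two-sided 5% with the CRC looks:

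- **N=60:** power is overstated by about 6 to 11 points where the weaker regimen is at 10–15% and the difference is 10 points or more. The overstatement is 2 to 3 points for a 5-point difference, and about 3 points or less where the weaker regimen is at 20% or more.
- **N=40:** power is understated by about 3 to 9 points where the weaker regimen is at 10% and by 1 to 2 points at 15%. In most rows at 20% or more it is overstated by about 1 to 2 points.
- **N=20:** power is understated by about 1 to 3.5 points with the weaker regimen at 10%, by 1 to 2 points at 15%, and by 1 point or less either way above that.

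A reader might infer that the whole table is optimistic. It is not: the direction changes with the stage and the response rate. These figures treat the guideline thresholds as firm gates, give power conditional on both cohorts reaching the stage, and assume equal cohort sizes.

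**What to change.** 1. In Section 11.8.3, state the test level as two-sided 5%, to match Section 11.5.1.2. Without this, a re-run would not give the figures above.
2. Re-run Table 11-9 with the Table 11-7 minima applied at n=10, 20 and 40 and the test at N=20, 40 and 60, separately for the CRC, TNBC and other-indication rules.
3. Add the probability that both cohorts reach each N (38% at N=60 for 10% v 25% under the CRC looks).
4. Replace the 0–52% power range and the 48–100% range for missing a difference with the new ranges. For the CRC looks the top is about 42%; it is lower for the other two rules.
5. Delete or reword the claim that the constraint reflects the expansion strategy.

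The cost is a re-run of an existing simulation under three rule sets, a revised table and a few sentences. No patients and no design change are involved. As the expansion part was not opened, the main use is to keep 52% from being carried into a report or a later protocol that reuses this design.

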12 DATA HANDLING AND RECORD KEEPING

12.1 Data Flow

Figure 12-1 Outline of Data Flow

12.2 Source Documentation

At a minimum, source documentation must be available for the following to confirm data collected in the eCRF: patient identification, eligibility, and trial identification; trial discussion and date of signed informed consent; dates of visits; results of safety and efficacy parameters as required by the protocol; record of all adverse events and follow-up of adverse events; concomitant medication; drug receipt/dispensing/return records; trial drug administration information; and date of trial completion and reason for early discontinuation of trial drug or withdrawal from the trial, if applicable.

In addition, the author of an entry in the source documents should be identifiable.

Specific details required as source data for the trial will be reviewed with the investigator before the trial and will be described in the monitoring guidelines (or other equivalent document).

12.3 Case Report Form Completion

Case report forms are provided for each patient in electronic format.

Electronic data capture (EDC) will be used for this trial. The trial data will be transcribed by trialsite personnel from the source documents onto an electronic CRF, and transmitted in a secure manner to the sponsor within the timeframe agreed upon between the sponsor and the trial site. The electronic file will be considered to be the CRF.

Worksheets may be used for the capture of some data to facilitate completion of the eCRF. Any such worksheets will become part of the patient's source documentation. All data relating to the trial must be recorded in eCRFs prepared by the sponsor. Data must be entered into eCRFs in English. Trial site personnel must complete the eCRF as soon as possible after a patient visit, and the forms should be available for review at the next scheduled monitoring visit.

All subjective measurements, such as ECOG will be completed by the same individual who made the initial baseline determinations whenever possible.

All eCRF entries, corrections, and alterations must be made by the investigator or other authorized trial-site personnel. The investigator must verify that all data entries in the eCRFs are accurate and correct. If necessary, queries will be generated in the EDC tool.

If corrections to an eCRF are needed after the initial entry into the eCRF, this can be done in three different ways:

- Trial-site personnel can make corrections in the EDC tool at their own initiative or as a response to an auto query (generated by the EDC tool).
- The monitor can generate a query for resolution by the trial-site personnel.
- The clinical data manager can generate a query for resolution by the trial-site personnel.
- The sponsor can generate a query for resolution by the trial-site personnel.

12.4 Data Quality Management

Steps to be taken to ensure the accuracy and reliability of data include the selection of qualified investigators and appropriate trial sites, review of protocol procedures with the investigator and trial-site personnel before the trial, periodic monitoring visits by the sponsor and direct transmission of clinical laboratory data from a central laboratory, ECG data from ECG vendor and CT-scans and reads from the scan vendor (expansion part only) into the sponsor's data base. Written instructions will be provided for collection, handling, storage, and shipment of samples.

Guidelines for eCRF completion will be provided and reviewed by the trial-site personnel before the start of the trial. The sponsor will review eCRFs for accuracy and completeness during on-site monitoring visits and after transmission to the sponsor; any discrepancies will be resolved with the investigator or designee, as appropriate. After upload of the data into the trial database they will be verified for accuracy and consistency with the data sources.

